## Study Duration, Subject Participation and Estimated Enrollment Period

The total study duration from , first patient, first visit, (FPFV) to last patient, last visit (LPLV) is expected to be 12 years, with a recruitment period of 24 months The investigator/investigative site must make every reasonable attempt to contact the patients to complete all scheduled post-operative visits within the visit window. In instances where the individual cannot be reached, the investigator/investigative site will document at least two attempts to contact the patient via phone/mail and one certified letter for each time point. Due to the length of this study and the risk of lost to follow-up potential, if a subject has an inability to and, for some unforeseen reason cannot be seen on the hospital site, patient reported outcome measure case report forms may be completed remotely by post or telephone and returned to the investigative site/investigator for review and submission. If this process is applied it must documented and reported to Wright accordingly.

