## **Device** Failure

Subjects will be considered a treatment failure, and will be withdrawn from the study if any sections of the device (tibial or talar metal components) have been removed at any time during their participation. This should be reported onto the adverse event form. In addition, any surgical intervention during study participation that relates to their total ankle replacement will be reported on the surgical intervention case report form.

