### STATISTICAL METHODS

### **General Considerations**

All enrolled subjects who underwent total ankle replacement implanted with INFINITY™ or INBONE® product configurations listed in Table 1 will be included in the analysis. All data will be summarized for all subjects at baseline and at every post-surgery visit, namely at 6 months, 1, 2, 5, 7, and 10 year post surgery.

Categorical data will be displayed as frequency and percent, and continuous data will be displayed using descriptive statistics (N, mean, standard deviation, quartiles, minimum and maximum, CI). Subgroup analyses will be conducted for all the patient reported outcomes: PROMIS Global Health AOS and FAOS. Subgroup analysis and comparisons will be presented for the following factors:

- surgical instrumentation type (standard vs additional approved instrumentation),
- type of primary disease diagnosis (Rheumatoid arthritis, Post traumatic, Degenerative);
- COFAS type (Types 1-4);
- Varus and/or valgus degree of deformity
- Radiographic radiolucency.

Radiolucency factors will be categorized independently with respect to linear and cystic radiolucency as follows:

Linear radiolucency:	Group 1: Present Linear radiolucency (>2mm)
	Group 2: Absent Linear radiolucency (>2mm)
Cystic radiolucency:	Group 1: Present Cystic radiolucency (>5mm)
	Group 2: Absent Cystic radiolucency (>5mm)

Subgroup analysis of the patient satisfaction of their total ankle replacement post operatively will only be done for surgical instrumentation type.

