### Survivorship of INFINITY® Total Ankle System

Survivorship of INFINITY® Total Ankle System will be based on secondary surgical intervention performed on the original implant. The Kaplan Meier survivorship method and life table analysis will be employed. Time to surgical intervention due to implant failure will be the survivorship endpoint of INFINITY® Total Ankle System. In addition, time to reoperation to exchange or remove any part of the INFINITY® Total Ankle System or surgical intervention due to failure of the implant as survivorship endpoint will also be analyzed. Subjects who did not undergo revision or reoperation due to implant failure at the time of reporting will be censored at the last follow-up. The Kaplan Meier survival curve with the 95% Confidence Interval will be constructed.

Year since	Number	Number of	Lost	Survival	95%
implantation	at start	failed implant		Rate	Confidence
					Interval
0-1	1		I		
1-2					
2-3					
3-4					
4-5					
5-6					
6-7					
7-8					
8-9					
9-10					

Table . Kaplan-Meier life-table survival of INFINITY® Total Ankle System.

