### Planned visits and Follow-Up Time Points

Subjects will be seen prospectively at the following intervals Pre-Op, Operative, 6 months, 1, 2, 5, 7, and 10 years. There are special circumstances where subjects required a visit outside the windows of the established visits, data collected from unscheduled visits will be included and analyzed. Data from an unscheduled visit maybe used to an adjacent missed visit.

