#### 2. Subsequent secondary surgical interventions

Adverse events that lead to secondary surgical intervention will be summarized, categorized by type of surgical intervention performed, namely: reoperation, reoperation with removal of implanted components, other interventions. The primary reason for the surgical intervention will be categorized as: implant failure, deep infection, aseptic loosening, subsidence, wound healing

Page 17 of 23

problems, bone fracture, non-union and other reasons will also be tabulated in the same manner.

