### 2. Report Timing of survivorship assessment

There will be two timepoints to assess and report survivorship, at the 5th (intermediate survivorship assessment) and 10th (long-term survivorship assessment) year follow-up.

At the intermediate assessment of survivorship (5th year follow-up), only patients with follow-up scores obtained at least four years after surgery will be included in the analysis. Patients who underwent reoperation or revision surgery with in four years of surgery will not be excluded. At the final assessment of survivorship (10th year follow-up), only patients with follow-up scores obtained at least eight years after surgery will be included in the analysis. Patients who underwent reoperation or revision surgery will be included in the analysis. Patients who underwent reoperation or revision surgery will be included in the analysis.

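### The 10-year survivorship rule drops failure-free patients without a score at 8 years or later but keeps every reoperated or revised patient, against the SAP's own censoring and all-subjects rules

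*SAP*

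**What the plan says.** The primary endpoint is Kaplan-Meier survivorship at 10 years (Protocol, Primary and Secondary Endpoints). Three parts of the SAP decide who enters that analysis.

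- **Other considerations, 2. Report Timing of survivorship assessment.** At 10 years, "only patients with follow-up scores obtained at least eight years after surgery will be included in the analysis". Reoperated or revised patients are then included with no time limit (that sentence is printed twice). The 5-year assessment has the same structure with a 4-year cut-off, but a narrower exemption: "Patients who underwent reoperation or revision surgery with in four years of surgery will not be excluded".
- **Survivorship of INFINITY® Total Ankle System.** "Subjects who did not undergo revision or reoperation due to implant failure at the time of reporting will be censored at the last follow-up". No minimum follow-up is set, and the life-table shell has a Lost column from year 0-1 onward.
- **General Considerations.** All enrolled subjects implanted with the "product configurations listed in Table 1 will be included in the analysis".

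Three further provisions matter. Neither document schedules a visit between 2 and 5 years or between 7 and 10 years, although under SAP Planned visits and Follow-Up Time Points "data collected from unscheduled visits will be included and analyzed". Under Protocol Device Failure a subject "will be withdrawn from the study if any sections of the device (tibial or talar metal components) have been removed". The Protocol section on study duration expects attrition ("Due to the length of this study and the risk of lost to follow-up potential") and allows questionnaires to be completed by post or telephone.

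**The concern.** The 10-year rule makes entry to the analysis depend on outcome. A patient whose implant fails at year 3 is kept. A patient followed failure-free to year 7 and then lost contributes nothing, although those seven years are valid Kaplan-Meier information. The entry ticket is also a score rather than known implant status, so a patient whose implant is known to be in place but who has no late questionnaire is dropped too. With the ±60-day windows (60/365.25 = 0.16 years), scheduled visits leave a gap from 7.16 to 9.84 years. The 8-year condition therefore mostly means completing the 10-year assessment or having a late unscheduled visit.

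The life table shows the conflict. Under the 10-year restriction the Lost cells for years 0-1 to 7-8 could hold only patients reoperated for a reason other than implant failure. Such reasons exist in the SAP: "The primary reason for the surgical intervention will be categorized as: implant failure, deep infection" and others.

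The 5-year rule has a further gap. Removal of a metal component in year 4-5 leads to withdrawal, and no visit is scheduled between 2.16 and 4.84 years. That patient may have no score at 4 years or later and falls outside the four-year exemption, so the failure is not clearly counted.

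Two analysts following this SAP could report different primary estimates, intervals and denominators, and the choice could be made after the data are seen.

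**Working it through.** **Inputs.** N = 155 (SAP, Study Design overview). The plan has no figure to reproduce: the Protocol says the sample size was not statistically calculated, and it states no target survival or attrition. Survival and loss rates below are assumptions.

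**Direction at 10 years.** S(t) = ∏(1 − d/n) over failure times, with d failures among n at risk. Every patient dropped is failure-free, so each d is unchanged and each n is equal or smaller. Each factor, and so S(10), is equal or lower. This needs every implant-failure intervention to count as reoperation or revision. In 20,000 random data sets with all failures kept there were no violations.

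**Worked example (illustrative data).** Twelve failures at 0.4, 0.9, 1.5, 1.9, 2.8, 3.7, 4.6, 5.4, 6.3, 7.6, 8.6 and 9.5 years. Lost: 3 at 0.5, 5 at 1, 8 at 2, 12 at 5 and 15 at 7 years. Seen at 10 years: 100. Total 12 + 43 + 100 = 155.

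- All subjects, censored at last follow-up: 154/155 × 150/151 × 143/145 × 132/135 × 118/120 × 100/103 = 90.9% (95% CI 85.9 to 95.8; half-width about 5 points).
- 10-year restriction: 12 + 100 = 112 patients, none censored before year 10, so the estimate is the crude proportion 100/112 = 89.3% (83.6 to 95.0).
- Lost column: 3, 5, 8, 12 and 15 in years 0-1, 1-2, 2-3, 5-6 and 7-8 under the censoring rule; zero in every row under the restriction.

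**Size over a range.** 3,000 simulated trials of 155 per scenario, constant hazards, loss unrelated to failure. Ranges cover loss measured by year 8 or by year 10, and follow-up that is continuous or ends at the last scheduled visit. Restricted minus all-subject estimate at 10 years, in percentage points:

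| True 10-year survival | 20% loss | 30% loss | 50% loss |
|---|---|---|---|
| 95% | -0.4 to -0.6 | -0.6 to -1.0 | -1.3 to -2.1 |
| 90% | -0.7 to -1.1 | -1.2 to -1.8 | -2.4 to -3.9 |
| 85% | -1.0 to -1.5 | -1.6 to -2.5 | -3.4 to -5.5 |

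The larger figure in the 50% column is 50% loss by year 8, which is 1 − 0.5^(10/8) = 58% by year 10. At 90% survival the analysed N falls to about 119-131 at 20% loss and 68-91 at 50%. Coverage of plain Greenwood 95% intervals at 90% survival is 93-95% at 20-30% loss (all-subject 93-94%) and 89-92% at 50%; at 85% survival and 50% loss it is 83-89%. If 10-20% of patients have a non-failure reoperation by year 10 and are kept as censored, the gap at 90% survival and 30% loss by year 8 shrinks only from -1.5/-1.8 to -1.3/-1.7.

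**If lost patients fail more often.** With twice the failure hazard in patients lost before year 8:

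| Loss by year 8 | Truth | Restricted | All-subject |
|---|---|---|---|
| 30% | 87.3% | 86.9-87.2% | 88.9% |
| 50% | 85.5% | 83.7-84.0% | 87.9-88.5% |

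Direction against the truth is then open, although the restricted estimate is still below the all-subject one.

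**5-year rule.** In the worked example the all-subject estimate is 154/155 × 150/151 × 143/145 × 132/135 = 95.2%. The restriction removes the 3 + 5 + 8 = 16 patients lost by year 2, leaving 139. With the 4.6-year failure kept, 132/139 = 95.0%; with it dropped, 132/138 = 95.7%. In simulation at 95% true 5-year survival and 20% loss by year 4, the gap is -0.4 to -0.5 points if all year 4-5 failures are kept, about 0 if half are dropped, and +0.5 if all are dropped.

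**The case against.** **The bound is conditional.** The SAP names the endpoint as surgical intervention for implant failure, and its list of secondary interventions has a separate class of other interventions, which the exemption does not cover. If some failures fall there and leave no late score, they are dropped and the estimate can rise. With 5 failures at 3 years and 5 non-exempt failures at 6 years, 5 patients lost at 7.5 years and 140 seen at 10, the all-subject estimate is 145/155 = 93.5% and the restricted one 140/145 = 96.6%. This stands as a condition on direction. The SAP's censoring sentence speaks only of revision or reoperation, which supports the reading used here. On the other reading the rule discards failures, which is no defence of it.

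**The sections can be read together.** Censoring could operate inside the restricted set, with the reporting-timing section as the specific rule. But the survivorship section is equally specific, and General Considerations still conflicts. If the restriction does prevail, an outcome-dependent set governs the primary endpoint. The Missing Data section does not settle it either: a censored time is usable data, not a missing value.

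**The shift is small.** At 20-30% loss it is under the interval half-width and barely affects coverage. The study has no hypothesis or performance goal, and the 50% loss rows rest on no figure in the documents. All true, and it limits the stakes. The error is still systematic, and the reported rate and denominator are themselves the primary result.

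**A score may be obtained remotely.** This reduces loss but does not change who is dropped.

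**The restricted estimate can be nearer the truth.** That happens when lost patients fail more often, but only because two errors offset by accident.

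**Conclusion.** The concern holds. The SAP gives incompatible analysis sets for the primary endpoint, and the one in the reporting-timing section selects on outcome. Subject to the condition on intervention type, the restricted 10-year estimate cannot exceed the all-subject estimate, whatever the attrition. It is biased downward against the truth when loss is unrelated to failure; otherwise that direction is open.

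The expected shift is about 1 to 2 points at moderate loss and 90% survival. It grows with loss and with lower survival, and interval coverage suffers materially only at about 50% loss. These sizes rest on assumed survival and loss rates and constant hazards.

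The 5-year part is a weaker claim: the rule selects on outcome and leaves failures in year 4-5 unclear, and its net effect can go either way. This must be corrected because it concerns the primary endpoint and the SAP cannot be executed unambiguously as written.

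**What to change.** In the section on report timing of survivorship, delete the 4-year and 8-year minimum-follow-up conditions and the requirement for scores. State instead that:

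- both the 5-year and 10-year Kaplan-Meier analyses use all implanted subjects, as in General Considerations;
- every failure up to the reporting time counts, including those in year 4-5 and those followed by withdrawal for component removal;
- each failure-free subject is censored at the last date on which implant status is known, whether or not a questionnaire exists (this makes the SAP's existing last-follow-up rule more precise);
- numbers at risk and lost are shown for each interval.

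The same edit should say which interventions count as failure, so that the endpoint, the censoring sentence and the list of secondary interventions agree. Any minimum-follow-up subset can remain as a labelled supplementary analysis.

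The cost is SAP wording only: no new data, and less programming than the filter requires.

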### **Missing Data**

Missing data will not be imputed. Patients who were missing data required for a given analysis will be excluded.

# **STANDARD ELEMENTS**

Wright Medical Technology, Inc.

Page: # of #

Protocol US17-TAR-001

Title of Display Study Population

## <BODY OF DISPLAY>

Data Version: <date9> Execution: <date9> <program name>

# **COMPUTING ENVIRONMENT**

All statistical analyses will be performed using SAS Version 9.4 or higher on a SAS PC platform.

## LISTING OF TABLES

Table	1.1	Subject Disposition
Table	1.2	All Protocol Deviations
Table	1.3	Demographics and Clinical Characteristics
Table	1.4	Medical History
Table	1.7	Surgical and Operative Information
Table	1.8	Additional Surgical Procedures Performed
Table	2.1	Life-table survivorship of INFINITY® Total Ankle System
Table	2.2.1	Ankle Osteoarthritis Score (AOS) by Instrumentation Type
Table	2.2.2	Ankle Osteoarthritis Score (AOS) Comparison by COFAS
Table	2.2.3	Ankle Osteoarthritis Score (AOS) by Disease Diagnosis
Table	2.2.4	Ankle Osteoarthritis Score (AOS) by Study Site
Table	2.2.5	Ankle Osteoarthritis Score (AOS) Comparison of Degenerative & Post-
Table	2.2.6	traumatic vs Inflammatory (RA) Ankle Osteoarthritis Score (AOS) Comparison by Degree of Valgus/Varus
		deformity
Table	2.2.7	Ankle Osteoarthritis Score (AOS) Comparison by Linear radiolucency
		(>2mm)
Table	2.2.8	Ankle Osteoarthritis Score (AOS) Comparison by Cystic Radiolucency
Table	2.3.1	(>5mm) PROMIS Global Health Score by Instrumentation Type
Table	2.3.2	PROMIS Global Health Score Comparison by COFAS
Table	2.3.3	PROMIS Global Health Score by Disease Diagnosis
Table	2.3.4	PROMIS Global Health Score by Study Site
Table	2.3.5	PROMIS Global Health Score Comparison of Degenerative & Post-traumatic
		vs Inflammatory (RA)
Table	2.3.6	PROMIS Global Health Score Comparison by Degree of Valgus/Varus
		deformity
Table	2.3.7	PROMIS Global Health Score Comparison by Linear radiolucency (>2mm)
Table	2.3.8	PROMIS Global Health Score Comparison by Cystic Radiolucency (>5mm)
Table	2.4.1	Foot and Ankle Outcome Score by Instrumentation Type
Table	2.4.2	Foot and Ankle Outcome Score Comparison by COFAS

Table	2.4.3	Foot and Ankle Outcome Score by Disease Diagnosis
Table	2.4.4	Foot and Ankle Outcome Score by Study Site
Table	2.4.5	Foot and Ankle Outcome Score Comparison of Degenerative & Post-
		traumatic vs Inflammatory (RA)
Table	2.4.6	Foot and Ankle Outcome Score Comparison by Degree of Valgus/Varus
		deformity
Table	2.4.7	Foot and Ankle Outcome Score Comparison by Linear radiolucency (>2mm)
Table	2.4.8	Foot and Ankle Outcome Score Comparison by Cystic Radiolucency
		(>5mm)
Table	2.5.1	Patient TAR satisfaction by visit and Instrumentation Type
Table	3.1	Radiographic Assessment by Visit
Table	3.2	Surgical Intervention by Visit
Table	4.1	Summary of Adverse Events – Treated Population
Table	4.2	Treatment Emergent Adverse Events
Table	4.3	Treatment Emergent Adverse events by visit
Table	4.4.1	Procedure Related Treatment Emergent Adverse Events
Table	4.4.2	Device Related Treatment Emergent Adverse Events
Table	4.5.1	Serious Treatment Emergent Adverse Events
Table	4.5.2	Procedure/Device Related Serious Treatment Emergent Adverse Events

### LISTING OF LISTINGS

- Listing 1 Demographic Information
- Listing 2 Study Population
- Listing 3 Inclusion/Exclusion Criteria
- Listing 4 Protocol Deviations
- Listing 5 Medical History
- Listing 8 Surgical and Operative Information
- Listing 9 Ankle Osteoarthritis Score (AOS)
- Listing 10 PROMIS Global Health Score
- Listing 11 AOS Score
- Listing 12 Radiographic Assessment
- Listing 13 Surgical Intervention
- Listing 14 Adverse Events
- Listing 15 Study Completion

### LISTING OF FIGURES

- Figure 1 Kaplan-Meier survival curve of INFINITY® Total Ankle System survivorship
- Figure 2 Time to Implant Failure, Long-term follow-up (10-year)
- Figure 3 AOS Scores by Visit
- Figure 4 PROMIS Global Health by Visit
- Figure 5 FAOS by Visit
